Accordingly, a multicenter, prospective, open-label study in the U.S. was initiated [2] (Preventative IVIG Therapy for CHB, PITCH). Enrollment criteria included the presence of anti-Ro Ab in the mother, birth of a previous child with CHB/neonatal lupus rash, current treatment with 20 mg/day of prednisone, and <12 weeks pregnant. IVIG (400 mg/kg) was given every 3 weeks from gestational week 12 - 24. The primary outcome was the development of 2nd or 3rd degree CHB. Twenty mothers completed the IVIG protocol before the predetermined stopping rule of 3 cases of advanced CHB was reached. CHB was detected at 19, 20, and 25 weeks; none occurred following a prolonged PR interval. One of these 3 mothers had 2 previous children with CHB. One child without CHB developed a transient rash consistent

with neonatal lupus. Sixteen children had no manifestations of neonatal lupus at birth. No significant changes in maternal titers of Ab to Ro60, Ro52, or La48 were detected over the course of therapy or at delivery. There were no safety issues.

In parallel with enrollment of the PITCH study, a European study was initiated in December, 2004. We and the P.I., [name], had agreed on the protocol. The study was terminated after 3 recurrent cases of CHB were identified following enrollment of 15 mothers [3]. Combining data generated from the U.S. and the European PITCH studies, there were 6 (18%) recurrences in 33 women who had previous pregnancies complicated by CHB. Each study was originally designed to conclude inefficacy of IVIG if 6 cases of 54 were identified. However, since the chances of one further recurrence in the next 21 (if combined US and UK) was greater than 98% assuming the 18% recurrence rate observed, the trial was deemed futile and terminated.

Hydroxychloroquine: A potential prophylactic approach

Antimalarials are among the most frequently prescribed medications in SLE patients. The prevention of flares and reduction of mortality are associated with the use of these medications as supported by a recent systematic review of high quality published evidence [20]. Serious adverse events such as cardiotoxicity are rare, even after prolonged use. With regard to retinal toxicity, CQ appears to be more toxic than HCQ [20].

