Another potential mechanism favoring efficacy in preventing CHB, is that HCQ by virtue of reducing endosomal acidification might also decrease transplacental transport of maternal antibodies. This possibility is supported by the fact that maternal IgG is pinocytosed at the apical surface of the syncytiotrophoblast into an acid endosomal compartment containing FcRn, and migrates via transport vesicles to the basolateral surface of the cell, where at physiologic pH it uncouples from the receptor (15).

Study Design

Nineteen women in Stage 1 and an additional 51 women in Stage 2 (if reached, for a total of 70 subjects) meeting eligibility criteria will receive 400mg per day of HCQ beginning as soon as pregnancy is established and informed consent obtained. Mothers already on HCQ will remain on 400mg, or escalate to 400mg if on 200mg. The primary investigator, [name]., holds a U.S. Federal Drug Administration-issued IND (Investigational New Drug) number (112357) for HCQ.

A. Screening visit: Prior to the qualifying visit, the consent form will be reviewed and signed. Laboratory tests will include: CBC, liver-function tests (routine chemistries; albumin will be important to standardize the effect of physiologic hemodilution of pregnancy in gauging changes in autoantibody titers), urinalysis, and a 24 h collection for measurement of creatinine clearance and protein excretion as deemed appropriate. Serologic profiles will include: measurement of ANA, anti-DNA, C3 and C4. Blood will be drawn for baseline anti-Ro/La titer HCQ level, and IFNαactivity. Only the former will be available prior to qualification for enrollment. In total, 35 ml of blood will be drawn at screening.

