Characteristics of the Research Population

Number of Subjects and Subject Recruitment

Stage 1, 19 subjects will be given HCQ. If fewer than 3 recurrences are observed, an additional 51 subjects will be treated in Stage 2 (Years 2-3, seeking a renewal and/or NIH funding). However, if 3 or more recurrences are observed after Stage 1, it will be concluded that HCQ is not effective in preventing CHB. Ultimately, HCQ will be considered efficacious for CHB if fewer than 6 CHB cases occur among 70 subjects evaluated on no potentially confounding medications.

While some subjects will be prescribed the study drug (HCQ) by the PI, [name], or a designated study team member (covered by Consent Form Version 1), many patients will be referred to the study from other sites. In these cases, patients' own doctors will take responsibility for prescribing the study drug, and patients will consent to have their bloods and medical records sent to the investigators at NYU for data and sample analysis (as delineated in Consent Form Version 2). [name] or another study team member will discuss the study with each potential subject and complete the informed consent process prior to enrollment. All subjects (74 in total) will be considered enrolled at NYU and consented using NYU IRB-approved consent forms.

Gender of Subjects

Because the aim of this study is to determine whether hydroxychloroquine use during pregnancy prevents congenital heart block, only female subjects will be recruited.

Age of Subjects

18-45

Racial and Ethnic Origin

No subject will be excluded from participation in this study on the basis of race or ethnic origin.

Eligibility (Inclusion) Criteria

1) Mothers must have anti-Ro and/or anti-La Ab documented in the NYU immunology laboratory (CLIA-approved), which utilizes an ELISA (Immunovision) as well as reactivity on ELISA to at least one of three recombinant antigens (48La, 52Ro, 60Ro, JB laboratory). [name] will likewise

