The proposed design has the following operating characteristics. Let p1 = recurrence rate definitely not worthy of further investigation; p2 = recurrence definitely worthy of further investigation. In this study, we define p1 = 18% [41] and p2 = 5%. According to Simon's optimal 2stage approach [32], the expected sample size is 29.8 subjects with a probability of early termination of 0.69 when the recurrence rate is equal to p1. The probability of accepting the treatment for further study is at most 5% if the recurrence rate is unacceptably high (>18%) with that treatment. In contrast, there is a 90% probability of accepting the treatment for further study if the true recurrence rate is 5%. It is important to emphasize that the purpose is to obtain critical data on the efficacy of HCQ in the prevention of recurrent CHB and determine whether this preventive approach should be studied further. At study completion, the proportion of mothers having a child with advanced CHB will also be computed, along with corresponding 95% confidence intervals. Secondary endpoints that are binary (i.e., occurrence of 1st degree block, abnormal fluid collection) will be analyzed by similar approaches. Continuous variables (e.g., shortening fraction, gestational age) will be summarized by estimating means and standard deviations. The effect of therapy on HCQ levels, IFN-α signatures, and Ab titers will be evaluated by fitting mixed effects linear models to repeated assessments of titers obtained during follow-up. In addition, change in any of these analytes at specific time points from baseline will be analyzed using the paired t-test or Wilcoxon signed rank test, depending on distribution of the data.

Safety committee. An independent DSMB will convene by teleconference three times during the year. The members include Drs. [name], [name], and [name] (all of whom served in PITCH).

Data Storage and Confidentiality

Data management. Study information will be recorded at the patients' obstetrical and rheumatology sites. Standardized, computer-adapted case report forms (CRFs) have been developed. Within 2 weeks of each visit, completed CRFs and tapes of the echocardiograms will be sent to [name]. Following review, CRFs will be faxed to the coordinator at NYU for final error checks and entered into the computer database. The coordinator will maintain a calendar for each patient, monitor completion

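### A pass on the single-arm rule is labelled efficacy, but the plan's error rates support only a decision to study HCQ further

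*Combined protocol and SAP*

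**What the plan says.** The final rule appears once, under Number of Subjects and Subject Recruitment: "HCQ will be considered efficacious for CHB if fewer than 6 CHB cases occur among 70 subjects", counting women evaluated without potentially confounding drugs. The sizes come from Study Design ("Nineteen women in Stage 1 and an additional 51 women in Stage 2 (if reached, for a total of 70 subjects") and the interim rule from the recruitment section ("If fewer than 3 recurrences are observed, an additional 51 subjects will be treated in Stage 2").

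The operating characteristics are under Statistical considerations for overall study: "In this study, we define p1 = 18% [41] and p2 = 5" (per cent). There the 5% and 90% are probabilities of accepting the treatment for more study, at recurrence rates of 18% and 5% respectively. The section goes on to stress that the purpose is to gather data on efficacy and to "determine whether this preventive approach should be studied further". It also plans the final recurrence proportion with a 95% confidence interval.

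The trial is described as open-label Phase II, with no concurrent control. The Specific Aim, like the recruitment section, is worded as settling whether HCQ prevents recurrence.

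**The concern.** Five or fewer cases in 70 means efficacy in one section and a case for further study in another. The efficacy sentence is the only statement of the final decision rule, so it is the one that a report would naturally follow.

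The two conclusions need different support. The binomial rule tests whether recurrence on HCQ is below a fixed 18%. Attributing a low rate to HCQ also requires that these women would have had about 18% recurrence without it, and a single arm cannot show that. The protocol recognises the problem elsewhere: Potential Benefits to the Subjects notes, of earlier chart-review data, that the treated mothers might have had unaffected babies anyway.

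The label matters because the opening section expects the results to become part of counselling for women with these antibodies who are considering pregnancy.

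**Working it through.** **Inputs.** Stage 1 n = 19, continue if at most 2 cases; Stage 2 n = 51, total 70; pass if at most 5 cases in all (Study Design; Number of Subjects and Subject Recruitment). Unacceptable rate 18%, promising rate 5% (Statistical considerations). I assume 70 evaluable women and apply the three-case stop at Stage 1 only, as the recruitment section does.

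**The plan's own figures.** The plan states: "the expected sample size is 29.8 subjects with a probability of early termination of 0.69 when the recurrence rate is equal to p1".

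- Early termination at 18% = 1 − P(X ≤ 2), X ~ Bin(19, 0.18) = 1 − (0.02304 + 0.09609 + 0.18984) = 0.691. This agrees.
- Type I error at 18% is 0.0075 (first row of the table). The stated ceiling of 5% is met with room to spare.
- Expected size = 19 + 0.309 × 51 = 34.8, and the pass probability at 5% is 0.3619 + 0.3357 + 0.1340 = 0.83. The stated 29.8 and 90% are not reproduced by the 70-subject rule. That is a separate matter, and nothing below depends on it.

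**Chance that an inert drug passes.** If HCQ does nothing, recurrence equals the background rate p, and

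P(pass) = Σ over x = 0, 1, 2 of P(Bin(19, p) = x) × P(Bin(51, p) ≤ 5 − x).

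| Background p | x = 0 | x = 1 | x = 2 | P(pass) |
|---|---|---|---|---|
| 18% | 0.02304 × 0.08332 = 0.00192 | 0.09609 × 0.03516 = 0.00338 | 0.18984 × 0.01182 = 0.00224 | 0.75% |
| 15% | 0.04560 × 0.20327 = 0.00927 | 0.15289 × 0.10220 = 0.01563 | 0.24283 × 0.04127 = 0.01002 | 3.5% |
| 14% | 0.05695 × 0.26339 = 0.01500 | 0.17614 × 0.14079 = 0.02480 | 0.25806 × 0.06068 = 0.01566 | 5.5% |
| 12% | 0.08814 × 0.41525 = 0.03660 | 0.22836 × 0.25194 = 0.05753 | 0.28026 × 0.12454 = 0.03490 | 12.9% |

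Solving P(pass) = 0.05 gives p = 0.142. Above that rate the error is below 5%, and it falls further as p rises.

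**What a bare pass shows.** 5/70 = 7.1%, with an exact (Clopper-Pearson) 95% interval of 2.4% to 15.9%, ignoring the two-stage sampling. The interval lies below a fixed 18%. It describes only the rate observed on HCQ and says nothing about the rate without it.

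**The case against.** The strongest reply is that the statistical section is worded correctly and with emphasis, the trial is labelled Phase II, and a confidence interval is planned. The missing control is also a disclosed choice: the protocol sizes a randomised comparison at 194 or 522 subjects before adopting a single arm. On this view the efficacy sentence is loose wording that another section already qualifies. All of this stands as a description of the design. It does not remove the inconsistency, because the sentence that overreaches is the one that states the decision rule.

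Two stronger readings are tempting, and the documents do not support either.

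- A reader might infer that the 5% error holds only if the background is exactly 18%, or fails as soon as it is slightly lower. For the printed rule it does not: the error is 3.5% at 15% and reaches 5% only at about 14.2%.
- A reader might infer that the 18% benchmark is shown to be imprecise, because the Background reports "there were 6 (18%) recurrences in 33 women who had previous pregnancies complicated by CHB", for which the exact 95% interval is 7.0% to 35.5%. Those women received IVIG, in two studies that each ended on reaching three cases. The statistical section cites a different source for 18% and gives no denominator. The precision of that benchmark is therefore unknown, and the 6/33 interval is only illustrative. The other rate the protocol uses, about 19%, is close to 18%.

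Nor does the protocol say that a pass would be reported as proof of efficacy. It says only that HCQ would be considered efficacious.

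**Conclusion.** The concern holds as an inconsistency in the stated conclusion. One section draws efficacy from fewer than 6 cases in 70. The section that defines the error rates draws only a decision on further study, and an uncontrolled comparison with a fixed 18% supports no more than that.

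The numerical exposure is moderate. An inert drug would pass with probability 0.75% at an 18% background, 3.5% at 15%, 5.5% at 14% and 12.9% at 12%. These figures rest on exact binomial sampling, 70 evaluable women and the printed cut-offs. Every background below 18% is an assumption, not an estimate from the documents. At 18%, and down to about 14.2%, the rule is at least as strict as the plan claims. The defect is the name given to a pass, not a breach of the 5% limit.

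**What to change.** 1. Under Number of Subjects and Subject Recruitment, replace *will be considered efficacious* with *will be considered worthy of further study*, so that the decision rule and the statistical section reach the same conclusion.
2. Beside the 18% figure, print the pass probability of the 70-subject rule for an inert drug: 0.75% at 18%, 3.5% at 15%, 5.5% at 14% and 12.9% at 12%. Label the lower rates as assumptions, and give the denominator and interval of the cited 18% if the source has them.
3. Report the final rate and its interval against that range of backgrounds, without an efficacy claim.

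The cost is one sentence and a four-row table, with no change to sample size, conduct or data collection. The drawback for the sponsor is a less favourable claim if the trial passes.

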Specific Aim: To determine whether hydroxychloroquine use during pregnancy prevents the recurrence of CHB.

This will be approached in an open label Phase II trial entitled: Preventative Approach to Therapy for Congenital Heart Block with Hydroxychloroquine (PATCH), in pregnant women who have had a previous child with CHB. This is designed as an open-label trial employing Simon's 2-stage optimal

design to allow for early stopping due to absence of treatment efficacy. The first stage requires 19 subjects, which are expected to be enrolled in the year of this award. Despite the rarity of disease and the requirement of a previous child with CHB, based on the US Research Registry for Neonatal Lupus (RRNL) and data from the UK, this proposal is feasible. If 3 mothers have a child with 2nd or 3rd degree CHB, the study is terminated after the first stage. Serial echocardiograms (monitor PR interval) and evaluation of biomarkers (HCQ levels, IFN*a* signatures, and Ab titers) will be part of the protocol. The results of this study should become an integral component of the counseling of women with anti-Ro/La Ab who are considering pregnancy.

Background

CHB associated with maternal anti-Ro Ab has a high mortality (20-30%, primarily fetal/neonatal) and morbidity (67% require permanent pacing before adulthood) [6,7]. In addition to conduction disease, 10-15% of affected offspring will have a life-threatening cardiomyopathy [8,9]. Histopathologic studies constitute a major basis for formulating hypotheses regarding the pathogenesis of CHB, which in turn guide the rationale for therapeutic approaches. Studies of several fetal hearts identified in utero with CHB or isolated myocarditis revealed that fibrosis is extensive and replaces the AV node, even in 20 and 22 week hearts [10], supporting the clinical observation that 3rd degree CHB is irreversible. The identification of a macrophage infiltration in fetuses dying most proximate to the time of diagnosis suggests that inflammation may be integral to the development of fibrosis [10].

Prenatal Considerations

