Safety committee. An independent DSMB will convene by teleconference three times during the year. The members include Drs. [name], [name], and [name] (all of whom served in PITCH).

Individual stopping rules: Fetal: 1) Development of advanced block (2nd or 3rd degree); 1st degree block will not constitute a formal stopping point. 2) Decrease of amniotic fluid index <5 cm. 3) Intrauterine growth restriction (IUGR) - no fetal growth over 2 weeks. 4) Hydrops or myocardial dysfunction or EFE. 5) Death. Maternal: 1) Serious reaction to study drug, e.g. severe rash or intractable G.I. intolerance. 2) Withdrawal of consent. If isolated 1st degree heart block occurs, dexamethasone may be offered, and the patient may continue in the study. If a patient achieves an individual stopping point due to CHB and hydropic changes, she will be offered dexamethasone and the outcome of the pregnancy will be prospectively followed.

Study stopping rules: Enrollment is stopped if 3 fetuses develop 2nd or 3rd degree block.

Potential Benefits to the Subjects

We hope that this study shows that treatment with hydroxychloroquine prevents the development of heart block in your baby.

The potential benefits are substantial in relation to the small risks posed by participation.

This study is important because there is information from basic science research suggesting that hydroxychloroquine may be effective in preventing the inflammation and fibrosis which may result in heart block. This is only testing done with test tubes, not animals or humans. There is also a large study that reviewed the charts of many women with anti-Ro antibodies and this study found that hydroxychloroquine may be beneficial. However, we also are not sure whether for those mothers who received hydroxychloroquine, they may have had normal babies even without taking the drug. The results of this study will be used not only for a potential benefit to your own baby but also as a guide to help other pregnancies in which the baby is at risk for heart disease.

Subject Identification, Recruitment and Consent/Assent

Method of Subject Identification and Recruitment

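### No rule closes Stage 2 enrollment once a sixth evaluable case has fixed a negative result, and the only study-level stop (three cases) has no stage limit and conflicts with the success criterion.

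*Combined protocol and SAP*

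**What the plan says.** **Success rule.** Number of Subjects and Subject Recruitment: HCQ will be considered efficacious "if fewer than 6 CHB cases occur among 70 subjects evaluated", with the sentence going on to limit the count to women on no potentially confounding medications. The maximum number of cases compatible with success is therefore five.

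**Stage 1 gate.** Same section: "If fewer than 3 recurrences are observed, an additional 51 subjects will be treated in Stage 2", and "if 3 or more recurrences are observed after Stage 1, it will be concluded that HCQ is not effective in preventing CHB". The Specific Aim gives the same threshold and ties it to the stage: "If 3 mothers have a child with 2nd or 3rd degree CHB, the study is terminated after the first stage".

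**Study-level stop.** Protection Against Risks, study stopping rules: "Enrollment is stopped if 3 fetuses develop 2nd or 3rd degree block". No stage is named.

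**Stage 2.** No section gives a numeric rule for closing enrollment within Stage 2. An independent DSMB is to meet three times during the year, with no case count attached to its review.

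**The concern.** The point at which Stage 2 can no longer succeed is known exactly in advance: the sixth case among women who count toward the criterion. If nothing closes enrollment then, further pregnant women, whom the protocol itself classes as vulnerable, would enter an open-label trial whose primary decision is already negative. Those not already on the study dose would start or escalate HCQ for the trial, and all would have its blood draws and serial fetal echocardiograms.

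The three-case rule does not settle the matter. If it covers both stages, it contradicts a criterion that accepts three, four or five cases. If it covers Stage 1 only, Stage 2 has no stop. The documents do not say which is meant.

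**Working it through.** **Inputs.** n1 = 19, continue with 0 to 2 cases; Stage 2 adds 51, N = 70; success with 5 or fewer (Study Design; Number of Subjects). Recurrence 18% (unacceptable) and 5% (worthwhile); stated expected N 29.8, early termination 0.69, acceptance at most 5% and 90% (Data Analysis And Data Monitoring).

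**1. The plan's own figures.** Let b be the binomial probability and B its cumulative sum.
- P(enter Stage 2) at 18% = b(0)+b(1)+b(2) for n = 19 = 0.0230 + 0.0961 + 0.1898 = 0.309. Early termination = 0.691, as stated.
- Expected N = 19 + 0.309 × 51 = 34.8, against the stated 29.8.
- Acceptance = Σ b(x; 19) × B(5−x; 51), x = 0, 1, 2. At 18%: 0.0230×0.0833 + 0.0961×0.0352 + 0.1898×0.0118 = 0.0075. At 5%: 0.3774×0.9589 + 0.3774×0.8896 + 0.1787×0.7494 = 0.831, against the stated 90%.
- With N = 54 and the same cut-offs: expected N = 19 + 0.309 × 35 = 29.8, acceptance 0.0493 at 18% and 0.903 at 5%. The stated figures therefore belong to 54 subjects, so results for both totals are given below.

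**2. Three-case rule read literally (both stages).** Reaching 70 then requires at most two cases. At 5%: P(X ≤ 2; 70) = 0.0276 + 0.1016 + 0.1845 = 0.31. Enrollment would usually end early even if HCQ worked as hoped.

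**3. Three-case rule confined to Stage 1, with closure at the sixth case.** P(sixth case by subject N, given Stage 2) = 1 − P(accept)/P(enter Stage 2). At 18%, N = 70: 1 − 0.00754/0.309 = 0.976. Subject-by-subject enumeration gives the mean position of the sixth case, taking all subjects as evaluable and each outcome as known before the next enrollment.

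| Rate, N | P(enter Stage 2) | P(sixth case, given Stage 2) | Mean subject | Avoided when it occurs | Averaged over all trials |
|---|---|---|---|---|---|
| 18%, 70 | 0.309 | 0.976 | 42.9 | 70 − 42.9 = 27.1 | 0.309×0.976×27.1 = 8.2 |
| 9%, 70 | 0.758 | 0.52 | 54.3 | 15.7 | 0.758×0.52×15.7 = 6.2 |
| 5%, 70 | 0.933 | 0.11 | 58.4 | 11.6 | 0.933×0.11×11.6 = 1.2 |
| 18%, 54 | 0.309 | 0.84 | 40.1 | 13.9 | 0.309×0.84×13.9 = 3.6 |

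At 18% and N = 70, expected N falls from 34.8 to 26.6.

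**4. Detection lag (assumption).** Stage 2 is placed in Years 2-3: 51 women / 104 weeks = 0.49 per week. With entry at 12 weeks and detection at 19 to 25 weeks (the range seen in the US IVIG study), 7 to 13 weeks × 0.49 = 3 to 6 women are enrolled before a case is seen. With a lag of 6, the conditional saving at 18% is about 21 (N = 70) or 8 (N = 54). The average over all trials at N = 70 is 6.4 at 18% (expected N 28.4) and 0.7 at 5%. Earlier entry lengthens the lag and reduces the saving further.

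**5. Acceptance.** A trial with six countable cases at any point has at least six at the end. Closing enrollment acts only on such trials, so both acceptance probabilities are unchanged.

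**The case against.** **A stop may already exist.** A reader might infer that the plan will certainly go on enrolling after a sixth case. The documents do not support that: the study stopping rule, taken at its word, ends enrollment at the third case in either stage. This stands. The consequence follows only if the three-case rule is confined to Stage 1, as the Specific Aim and recruitment section suggest.

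**Not every sixth case is decisive.** A reader might also infer that any sixth case settles the result. The criterion counts only women on no potentially confounding medications, women with first-degree block may receive dexamethasone and remain in the study, and the recruitment section also gives a total of 74. A raw count of six could close a trial that might still succeed. This stands, and the rule must count evaluable cases only.

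**The design is valid without it.** A Simon two-stage design needs no stop within a stage, a DSMB oversees the trial, and later women would still inform the recurrence estimate, secondary outcomes and biomarker models. All true; none of it gives Stage 2 a numeric rule.

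**The IVIG precedent is limited.** It would be wrong to say those trials had no rule. The US study reached a predetermined three-case stop and the European one ended after three recurrences. The statement that "the trial was deemed futile and terminated" rests on an argument from the combined data about reaching six of 54.

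**Conclusion.** The point holds in a conditional form. The three-case rule and the fewer-than-six criterion cannot both govern Stage 2 and must be reconciled. If the three-case rule is a Stage 1 rule, Stage 2 lacks a closing point that is exactly known and costs nothing in error rates.

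The figure of 27 avoided enrollments is not an expected saving. It applies at 18% recurrence, with N = 70, in trials that reach Stage 2 and meet a sixth case. Over all trials the saving at 18% is about 8 women (6 with lag), and at 5% about 1. It is smaller if the total is 54. The calculations assume independent outcomes, all subjects evaluable, and an accrual rate inferred from the Stage 2 timetable.

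This is an efficiency and ethics improvement. Nothing here shows that the two-stage test is invalid.

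**What to change.** 1. Reconcile the Specific Aim, Number of Subjects and Subject Recruitment, and the study stopping rules by stating which stage the three-case rule covers.
2. If it is Stage 1 only, add to the recruitment section and the study stopping rules: *In Stage 2, enrollment closes when the sixth confirmed case occurs among subjects who count toward the primary criterion; women already enrolled are followed to outcome and included in the reported proportion.*
3. Define who counts toward the criterion, so that the sixth case can be recognized when it occurs, and settle whether the total is 70 or 54.

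The cost is a few sentences. In trials that close early, the confidence interval is wider, the naive recurrence proportion is biased somewhat upward because enrollment ends on an event (a fixed-sample interval then no longer strictly applies), and there are fewer secondary and biomarker data. These losses fall only on trials whose primary decision is already negative.
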